6.5 Trial allocation

After the patient has signed the consent form, the site will assign a unique patient number through the EDC system. Once assigned, it becomes the permanent trial identifier for that patient. A patient number cannot be re-used for any reason. If the patient is re-screened a new unique patient number will be assigned.

Trial participation begins once written informed consent is obtained. Refer to Section 10.3 for details on the informed consent process. Once informed consent is obtained, the screening evaluations to assess eligibility criteria may begin.

Patients that fulfill all inclusion and none of the exclusion criteria will be offered to be enrolled in the trial.

6.6 Trial Intervention Compliance

When the individual dose for a patient is prepared from a bulk supply, the preparation of the dose should be confirmed by a second member of the trial site staff.

Patients are dosed at the hospital site or clinic, hence they will receive trial intervention directly from the investigator or designee, under medical supervision. The date and time of each dose administered will be recorded in the source documents and eCRF. The dose of trial intervention and trial patient identification will be confirmed at the time of dosing by a member of the trial site staff other than the person administering the trial intervention.

A record of the quantity of IMP administered to each patient must be maintained and reconciled with trial intervention and compliance records. Intervention start and stop dates, including dates and reason for intervention delays and/or dose reductions will also be recorded.

Clinical Study: ES2B-C001-S01 EU CT No.: 2024-516333-12-00

6.7 Medication Errors

Medication errors and uses outside what is foreseen in the protocol may include:

- Administration of wrong drug
- Wrong route of administration, i.e. not IM
- Accidental administration of a lower or higher dose than intended. An overdose is defined
 as a patient receiving a dose of adjuvanted or non-adjuvanted ES2B-C001 exceeding 10%
 as compared to the protocol-specified dose. An underdose is defined as a patient receiving
 a dose of adjuvanted or non-adjuvanted ES2B-C001 less than 10% as compared to the
 protocol-specified dose.

If a medication error results in an AE, the AE must also be reported in the eCRF. If the event qualifies as a SAE, it must be reported as described in Section 12.4.

6.8 Continued Access to Trial Intervention after the End of the Trial

Patients will be considered to have completed the study protocol if they attend an end of study (EOS) visit 6 weeks after the last dose of the primary vaccination series.

Booster doses may be offered to patients under a compassionate use program (CUP) based on the investigator's choice to patients with at least stable disease or better who show a good immunologic response and a good tolerability, if they wish to receive such boosters.

6.9 Prior and Concomitant Therapy

6.9.1 Prior Medications

The investigator or qualified designee will review prior medication use, including any protocolspecified washout requirement, and record in the eCRF prior medication taken by the patient during the past 2 months.

All previous lines of anti-cancer therapy must be documented in the eCRF at baseline, including previous CHT regimens and neoadjuvant or adjuvant treatment given at time of primary diagnosis of breast cancer, if applicable.

6.9.2 Concomitant Therapy

Concomitant therapy consists of any medications (including prescription drugs, OTC drugs, nutritional supplements, herbal or homeopathic remedies) used by the patient between Day -28 and End of Study (EOS) in addition to protocol mandated treatment.

Medications or vaccinations prohibited in the exclusion criteria are not allowed during the ongoing trial. If there is a clinical indication for any medication or vaccination specifically prohibited during the trial, discontinuation from ES2B-C001 may be required and will be evaluated by the medical monitor and agreed with Sponsor on a case-by-case basis.

[figure not shown]
The investigator is to discuss prohibited medication/vaccination with the Sponsor. The final decision on any supportive therapy or vaccination rests with the investigator and/or the patient's

Clinical Study: ES2B-C001-S01 EU CT No.: 2024-516333-12-00

primary physician. However, the decision to continue the patient on trial treatment requires the mutual agreement of the investigator, the Sponsor, and the patient.

Listed below are specific restrictions for concomitant therapy or vaccination during the course of the trial:

All concomitant medication should be recorded in the eCRF.

6.9.3 Rescue Medicine

Due to the potential of autoimmunity as response to the vaccine with self-antigen (HER2), start of rescue treatment according to institutional standard, must be evaluated and started without delay by the treating physician (or a medically qualified delegate on-site).

Local and systemic AEs related to the adjuvanted ES2B-C001 injection should be treated symptomatically to relieve the patients as deemed necessary by the treating physician (or a medically qualified delegate on-site).

In case of suspected immune system disorders, such as hypersensitivity, allergic reaction/anaphylaxis or autoimmune disease symptomatic supportive treatment as needed (care guided by organ specific symptoms) should be provided as well as and rescue treatment to brake immune response, these may include antihistamines, steroids, and any standard acute treatment regimens for anaphylactic shock as per local practice.

Symptomatic suspected cancer therapy-related cardiac dysfunction (CTRCD) should be handled according to the local best practice, including referral to cardiologist as needed. Symptomatic heart failure should be treated according to current international guidelines, e.g. "2021 ESC Guidelines for the diagnosis and treatment of acute and chronic heart failure"

Clinical Study: ES2B-C001-S01 EU CT No.: 2024-516333-12-00

The use of rescue medications is allowable at any time during the trial. The date and time of rescue medication administration as well as the name and dosage regimen of the rescue medication must be recorded and linked to relevant AEs in the eCRF.

7 Discontinuation and delaying of Trial Intervention and Patient Discontinuation/ Withdrawal

7.1 Discontinuation of Trial Treatment

Patients may stop treatment at any time during the trial at their discretion. The treating physician may, for safety reasons or the well-being of the patient, refrain from dosing at the discretion of the treating physician.

If adjuvanted or non-adjuvanted ES2B-C001 is permanently discontinued, the patient should, if at all possible, have an early termination visit and remain in the trial for follow-up visit 7 and 8. See the SoA (Section 1.3) for data to be collected at the End of Trial and during follow-up.

Discontinuation of trial treatment does not represent withdrawal from the trial.

Patients who discontinue for reasons other than toxicity before having DLT evaluable safety data may be replaced at sponsor's discretion.

A patient should be considered for discontinuation from trial treatment but continue to be monitored in the trial for any of the following reasons:

- Unacceptable toxicity.
- Intercurrent illness of sufficient magnitude to preclude safe continuation of the trial.
- Investigator's judgement on optimal benefit/risk not supporting continuation of the trial for the individual patient.
- Non-compliance with trial requirements (e.g. treatment delay of 28 days or more).
- · Patient's decision.
- Pregnancy during the trial.
- Patient is lost to follow-up.
- Death.

7.2 Temporary Discontinuation of Trial Treatment

Patients experiencing a symptomatic decline in organ function suspected to be related to (adjuvanted) ES2B-C001 must be evaluated by the investigator and submitted to treatment pause as needed.

Declines in organ function that a are not symptomatic, not clinically significant and/or discovered only through routine testing, without associated clinical symptoms should not lead to treatment pauses.

Clinical Study: ES2B-C001-S01 EU CT No.: 2024-516333-12-00

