4.3.1 Dose escalation rules

Dose escalation to a higher dose will be driven by an evaluation by the DSMB. At the time of DSMB evaluation, the last patient in the current dose level cohort must have received the 2nd dose and must have accumulated safety data for 8 weeks following the first dose. This allows for the DLT evaluation period to include an assessment of a potential delay in dose 2 due to toxicity concerns, as described for DLT number 5 in Section 4.3.2.

If one of the 3 patients in a dosing cohort experiences a DLT, 3 additional patients are added to the same dose level cohort. If 2 or more patients among these 6 patients experience DLTs, no further dose escalation can occur, and lower dose levels can be further explored. Dose escalation will continue until not more than 1 out of 6 patients experience DLT in a dose level cohort or the highest dose level group has completed treatment or no trial stopping criterion has been met. See Figure 2.

[figure not shown]

Figure 2: Dose-escalation according to a 3+3 design

Dose escalation will continue until not more than 1 out of 6 patients experiences a DLT in a dose level cohort (see DLT definitions in Section 4.3.2) or the dose level of

Clinical Study: ES2B-C001-S01 EU CT No.: 2024-516333-12-00

treatment has been completed (maximum administered dose MAD) or a trial stopping criterion has been met. The stopping criteria for dose escalation and trial are provided in Section 7.

Patients experiencing DLT will have their administration of adjuvanted or non-adjuvanted ES2B-C001 discontinued. These patients are allowed to remain in the trial to follow safety, disease progression and immune response. The DSMB will convene and recommend whether a re-start of these patients' treatment is advised and if a dose reduction may be required.

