4.3.2 Definition of Dose-limiting Toxicity (DLT)

A DLT is defined as any grade \geq 3 AE according to the NCI-CTCAE v. 5.0 observed at any time from the first administration of ES2B-C001 (alone or adjuvanted) to the 8 weeks thereafter, which despite standard supportive care and in the opinion of the Investigator, is possibly, probably, or definitely related to adjuvanted or non-adjuvanted ES2B-C001, or other event as described below. Investigators evaluation of relatedness to trial treatment administration should take concomitant medication into account.

DLTs will include:

- 1. Any grade ≥ 3 adverse events except:
 - a. Grade ≥ 3 nausea, vomiting, or diarrhea lasting ≤ 72hours with optimal medical therapy Grade 3 fatigue or anorexia lasting < 7 days.
 - b. Fever that occurs within 48 hours of IMP administration and resolves to Grade 2 within 48 hours and is fully resolved within 7 days.
 - c. Non-clinically relevant isolated biochemical abnormalities (e.g., isolated increase in gamma-glutamyltransferase [GGT]).
 - d. Laboratory values out of normal range without related clinical symptoms, clinically transient isolated in nature.
 - e. Laboratory abnormality that is asymptomatic and deemed by the Investigator not to be clinically significant.
- 2. Grade 3 autoimmune reactions, except Grade 3 autoimmune thyroiditis or other endocrine abnormality that can be managed by endocrine therapy.
- 3. Intolerable or > grade 3 injection-site reactions according to FDA guidance 2007 (table 16 appendix 2).
- 4. Grade 2 decrease in left ventricular ejection fraction (LVEF).
- 5. Treatment delay of >14 days due to any related adverse event(s).

In any case, the reported toxicity should be discussed between the Investigators and both the DSMB and the Sponsor. All toxicities will be graded using NCI-CTCAE Version 5.0 based on investigator assessment.

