7.2.1 Cancer therapy-related cardiac dysfunction

Symptomatic suspected cancer therapy-related cardiac dysfunction (CTRCD) should be handled according to the local best practice and include referral to cardiologist as needed.

Moderate and severe asymptomatic suspected CTRCD, as defined in the 2022 ESC cardiooncology guidelines see Table 12, should lead to pause of trial treatment and referral to cardiologist.

Table 12: Definition of Asymptomatic cancer therapy-related cardiovascular toxicity

Severe	New LVEF reduction to <40% or reduction by ≥20 percentage points from baseline
Moderate	New LVEF reduction by ≥10 percentage points to an LVEF of 40–49% OR New LVEF reduction by <10 percentage points to an LVEF of 40–49% AND either new relative decline in GLS by >15% from baseline OR new rise in cardiac biomarkers
Mild	LVEF ≥ 50% AND new relative decline in GLS by >15% from baseline AND/OR new rise in cardiac biomarkers

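### Section 7.2 and its subsection 7.2.1 give opposite instructions on pausing treatment for a moderate or severe LVEF fall that is asymptomatic and found at the scheduled echocardiogram

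*Protocol*

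**What the plan says.** Section 7.2 (Temporary Discontinuation of Trial Treatment) first deals with symptomatic declines suspected to be related to the vaccine, which are to be evaluated and paused as needed. It then turns to the remainder. The subject of that sentence is "Declines in organ function that a are not symptomatic, not clinically significant and/or" and it continues "discovered only through routine testing, without associated clinical symptoms should not lead to treatment pauses". No organ is excepted and no subsection is cited.

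Section 7.2.1 (Cancer therapy-related cardiac dysfunction) says of "Moderate and severe asymptomatic suspected CTRCD", as defined in Table 12, that it "should lead to pause of trial treatment and referral to cardiologist". In Table 12, moderate includes "New LVEF reduction by ≥10 percentage points to an LVEF of 40–49" per cent, and severe is "New LVEF reduction to <40% or reduction by ≥20 percentage points from baseline".

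Section 8.3.5.2 plans echocardiography at baseline and again before the fifth dose, at week 12 (+/- 7 days). No other on-treatment echocardiogram appears in the readable text.

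Two further rules bear on the same measurement. DLT criterion 4 in Section 4.3.2 counts a "Grade 2 decrease in left ventricular ejection fraction (LVEF") as a DLT and states no symptom requirement. Section 4.3.1 adds: "Patients experiencing DLT will have their administration of adjuvanted or non-adjuvanted ES2B-C001 discontinued". The DSMB then advises on any restart.

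**The concern.** An LVEF fall is a decline in organ function. Every patient covered by Table 12 is asymptomatic by the table's own title, and the planned echocardiogram is a routine test. The patients whom 7.2.1 pauses therefore have the very features that 7.2 gives as reasons for not pausing. Both sentences use 'should' for the same action, so neither is the weaker instruction.

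What is at stake is a dosing decision in a first-in-human trial, on the organ that the protocol itself watches. Section 2.3 notes HER2 expression in normal heart and commits to cardiac evaluation throughout the study, and Section 12.3 lists CTRCD as an event of special interest. A site could follow 7.2 as written and give a dose that 7.2.1 says to hold, and either action could be recorded as a departure from the protocol. The same finding could also be handled differently from patient to patient.

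**Working it through.** The plan states no figure on this point. The check applies both rules to the same finding.

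**Inputs**
- 7.2, scope: declines that are asymptomatic, not clinically significant 'and/or' found only by routine testing without symptoms. Action: no pause.
- 7.2.1, scope: asymptomatic suspected CTRCD, moderate or severe in Table 12. Action: pause and cardiology referral.
- Table 12: moderate includes a fall of at least 10 points to 40–49%; severe is below 40% or a fall of at least 20 points; mild has LVEF of at least 50%.
- 8.3.5.2: on-treatment echocardiogram at week 12 +/- 7 days, before dose 5.
- 4.3.1 and 4.3.2: DLT window of 8 weeks from the first dose.

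**Step 1: one finding under both rules.** The LVEF values are assumed, since the protocol gives no example. All cases are symptom-free and found at the planned echocardiogram.

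| Baseline to week 12 | Fall | Table 12 | 7.2.1 | 7.2, read with 'or' |
|---|---|---|---|---|
| 60% to 45% | 60 − 45 = 15 points | Moderate (at least 10, to 40–49%) | Pause, refer | No pause |
| 60% to 38% | 60 − 38 = 22 points | Severe (below 40%; also at least 20) | Pause, refer | No pause |
| LVEF still at least 50%, with the GLS or biomarker change in Table 12 and a fall below 20 points | n/a | Mild | No pause stated | No pause |

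The first two rows conflict and the third does not.

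**Step 2: does the conflict depend on how 7.2 is read?**
- With 'or', lack of symptoms together with routine detection is enough, and the conflict is complete.
- With 'and', a decline must also be not clinically significant. A moderate or severe fall then leaves the scope of 7.2 only if someone judges it clinically significant. The protocol does not define that term for this purpose or tie it to Table 12.
- If 7.2.1 overrides 7.2, there is no conflict. No wording in either section says that it does.

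The conflict disappears only on a reading that the site has to supply.

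**Step 3: does it reach the DLT endpoint?** The earliest planned on-treatment echocardiogram is at 12 − 1 = 11 weeks. The DLT window closes at 8 weeks. The gap is at least 11 − 8 = 3 weeks, so a fall found at that visit, and any hold that follows, comes after the window.

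**The case against.** The best defence is structural. Section 7.2.1 sits under 7.2, follows it directly and names the exact case. Section 7.2.2 likewise sets specific pause triggers under the same heading. The natural reading is a general default followed by organ-specific rules, and the absence of a pause for mild CTRCD fits that. In addition, 7.2 speaks of declines that are not clinically significant, and a finding that calls for cardiology referral is hard to describe in that way. Other safeguards exist: the physician may refrain from dosing (7.1), CTRCD is reported to the sponsor within 24 hours (12.3 and 8.4.1), and safety concerns go to the DSMB (4.3 and 10.7).

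Much of this stands. A careful reader may well arrive at the override. But it has to be inferred, because 7.2 contains no exception and the 'and/or' permits the broad reading. Discretion and reporting allow a pause; they do not settle which of two opposing instructions applies.

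A reader might go further in two directions that the documents do not support. The first is that the primary DLT endpoint depends on which section a site follows, through criterion 4 or through criterion 5 (related delay of more than 14 days). On the stated schedule the on-treatment echocardiogram falls after the DLT window. The schedule of activities is not readable in the public text, so an earlier planned echocardiogram cannot be asserted. The second is that the DLT rule conflicts with 7.2.1. Discontinuation with DSMB advice on restart is compatible with a pause and referral, and one scale for management beside another for DLT classification is not in itself an error. The CTCAE thresholds for LVEF are not in the protocol (Table 15 is generic), so the two scales cannot be compared here.

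**Conclusion.** The point holds as a safety-relevant wording inconsistency. For moderate and severe asymptomatic CTRCD found only at the planned echocardiogram, 7.2 read literally says not to pause and 7.2.1 says to pause. On the readable schedule this touches one decision per patient, namely whether the fifth dose is given at about week 12. Mild CTRCD is unaffected.

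DLT criterion 4 is a side issue. Because it has no symptom requirement and 4.3.1 discontinues dosing after a DLT, it also sits awkwardly with the no-pause sentence in 7.2 if LVEF happens to be measured within the first 8 weeks. That is a reason to cover it in the same clarification. It is not evidence that the DLT endpoint is compromised.

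The conclusion rests on the literal 'and/or', on the absence of any exception or cross-reference in 7.2 and 7.2.1, and on 8.3.5.2 as the source for echocardiogram timing. The LVEF values are illustrative. No view is taken on which clinical rule is right.

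**What to change.** Reconcile the passages in the protocol text:

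- In 7.2, state whether the no-pause sentence applies to cardiac findings covered by 7.2.1 and Table 12.
- In 7.2, replace the 'and/or' with wording that makes clear whether the conditions are cumulative or alternative. If clinical significance is a condition, say how it relates to the Table 12 classes.
- State how the no-pause sentence relates to DLT criterion 4 and to discontinuation after a DLT in 4.3.1, with a cross-reference between 7.2.1 and criterion 4.

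The sponsor and the DSMB decide which rule stands; the aim is that each LVEF result leads to one action. The cost is a wording amendment to 7.2 and 7.2.1, with no new procedure, visit or patient.

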7.2.1 Cancer therapy-related cardiac dysfunction

Symptomatic suspected cancer therapy-related cardiac dysfunction (CTRCD) should be handled according to the local best practice and include referral to cardiologist as needed.

Moderate and severe asymptomatic suspected CTRCD, as defined in the 2022 ESC cardiooncology guidelines see Table 12, should lead to pause of trial treatment and referral to cardiologist.

Table 12: Definition of Asymptomatic cancer therapy-related cardiovascular toxicity

Severe	New LVEF reduction to <40% or reduction by ≥20 percentage points from baseline
Moderate	New LVEF reduction by ≥10 percentage points to an LVEF of 40–49% OR New LVEF reduction by <10 percentage points to an LVEF of 40–49% AND either new relative decline in GLS by >15% from baseline OR new rise in cardiac biomarkers
Mild	LVEF ≥ 50% AND new relative decline in GLS by >15% from baseline AND/OR new rise in cardiac biomarkers

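### Sections 7.2, 7.2.1 and 6.9.3 order the pause and referral rules for symptomatic and asymptomatic suspected cardiac dysfunction inconsistently

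*Protocol*

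**What the plan says.** Three places in the protocol govern dosing and referral when cardiac dysfunction is suspected.

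- Section 7.2, the general rule on organ function. A patient with a symptomatic decline suspected to be related to the product "must be evaluated by the investigator and submitted to treatment pause as needed". Declines that are not symptomatic, not clinically significant and/or "discovered only through routine testing, without associated clinical symptoms should not lead to treatment pauses".
- Section 7.2.1, the cardiac rule. For symptomatic suspected CTRCD: "Symptomatic suspected cancer therapy-related cardiac dysfunction (CTRCD) should be handled according to the local best practice and include referral to cardiologist as needed". For the other presentation, "Moderate and severe asymptomatic suspected CTRCD" as defined in Table 12 "should lead to pause of trial treatment and referral to cardiologist". Table 12 also defines a mild asymptomatic class, but no action is attached to it. The table has no symptomatic class.
- Section 6.9.3, rescue medicine. Symptomatic suspected CTRCD "should be handled according to the local best practice, including referral to cardiologist as needed". No pause is mentioned.

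Two other parts of the protocol bear on this. Section 4.3.2 makes a Grade 2 LVEF decrease (item 4), and related events of grade 3 or above with listed exceptions, a DLT within 8 weeks of the first administration. Section 4.3.1 then discontinues administration, and the DSMB advises on any restart. Section 8.3.5.2 places the on-treatment echocardiogram at week 12, give or take 7 days, before the fifth dose.

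**The concern.** A parent section and its subsection should point the same way. Here 7.2 makes symptoms the ground for pausing, while 7.2.1 gives its firm instruction to patients without symptoms and leaves those with symptoms to local practice. A site that follows 7.2.1 literally has a definite instruction for a silent LVEF fall and none on dosing for the same fall with symptoms. A site that follows 7.2 would do the opposite with the silent fall.

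What is at stake is uniform application of a dosing-safety rule in a first-in-human trial. CTRCD is one of three listed adverse events of special interest (section 12.3), and section 2.3 offers cardiac monitoring throughout the study as a safeguard. If the rule can be read two ways, similar patients in one small cohort may be dosed differently, and the safety data by dose level become harder to interpret.

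**Working it through.** No sample size, power or error rate enters, and the plan states no figure to reproduce. The check sets the rules side by side.

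| Presentation | 7.2 (general) | 7.2.1 (cardiac) | 6.9.3 |
|---|---|---|---|
| Symptomatic | Evaluation mandatory, pause conditional | Local practice, referral conditional, no pause stated | Referral conditional, no pause stated |
| Asymptomatic, moderate or severe | No pause | Pause and referral, no condition | Not addressed |
| Asymptomatic, mild | No pause | Defined in Table 12, no action stated | Not addressed |

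Step 1: the two orderings. Down the 7.2 column, the firmer action belongs to the symptomatic patient. Down the 7.2.1 column, it belongs to the moderate or severe asymptomatic patient. The two columns also conflict directly for that second group.

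Step 2: an example using Table 12. Suppose LVEF falls from 60% to 45%. The reduction is 60 − 45 = 15 percentage points. That is at least 10 points, ends within 40–49%, and meets neither severe criterion (below 40%, or a fall of 20 points or more), so the class is Moderate. Without symptoms, 7.2.1 gives pause and referral. With symptoms, 7.2.1 gives referral if needed, and any pause must be drawn from 7.2, again if needed.

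Step 3: whether the DLT rule closes the gap. Item 4 and the grade 3 rule do not depend on symptoms, so a qualifying event stops administration in either presentation. The protocol does not print the LVEF limits for Grade 2, so the example is not graded here. The DLT period is 8 weeks from first dose. The named echocardiogram is at week 12 ± 1 week, so at week 11 at the earliest, which is 11 − 8 = 3 weeks after that period ends. The DLT rule therefore does not govern the dosing decision that this echocardiogram precedes.

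Step 4: what applies at week 12. Sections 7.2 and 7.2.1 are the specific cardiac dosing rules. Section 7.1 lets the treating physician withhold a dose and lists unacceptable toxicity as a reason to consider discontinuation. Section 10.7 sends safety concerns to the DSMB throughout the trial. None of these states which ordering applies.

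**The case against.** The best defence is that symptomatic and asymptomatic patients are disjoint groups, so both sentences of 7.2.1 can be obeyed together. Fixed thresholds for silent findings, with clinical judgement for patients who feel ill, is a coherent design. This stands for 7.2.1 read alone. It does not explain why the parent section says that silent declines should not cause pauses. One could read 7.2 narrowly, as sparing only declines that are both silent and clinically unimportant, but its and/or wording does not say so.

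A second defence is oversight. CTRCD is an event of special interest, reported to the sponsor within 24 hours (8.4.1), and events that may call for rescue medication go to the DSMB (4.3, 10.7). This also stands. A reader might infer that a symptomatic patient could be redosed on one physician's unreviewed decision, or that 7.2.1 is the only safeguard after week 8. The documents support neither. These provisions supply review and reporting, however, and not a pause rule.

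A reader might also infer that the primary endpoint is biased, because a pause prescribed for silent cases could become a DLT through item 5 (a related delay of more than 14 days) while a discretionary non-pause could not. The documents do not support this. Item 4 counts a Grade 2 LVEF decrease with or without symptoms. The echocardiogram named in 8.3.5.2 falls after the DLT period, so nothing named there would reveal a silent fall within it, whereas symptoms would prompt evaluation.

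**Conclusion.** The inconsistency is in the current text. Section 7.2 ties pauses to symptoms, 7.2.1 gives its unconditional pause and referral to moderate and severe asymptomatic cases only, and 6.9.3 repeats the conditional referral for symptomatic ones. No other section resolves it.

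Its reach is limited. The firm instruction is worded as should, so it would be wrong to infer that asymptomatic cases must be paused, and mild cases are outside it. The only must in these rules concerns evaluating the symptomatic patient. No analysis, sample size or DLT count is shown to change. The effect is on how consistently dosing is handled for one listed event of special interest, chiefly around the fifth dose.

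The conclusion on timing assumes that 8.3.5.2 names all scheduled on-treatment echocardiograms. The schedule of activities could not be read here, and an earlier one listed there would soften step 3 but leave the conflict between sections. It would also go too far to conclude which presentation should carry the firmer action, because that is a clinical decision.

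**What to change.** Reconcile 7.2, 7.2.1 and 6.9.3 with each other and with the DLT provisions in 4.3.1 and 4.3.2. State in one place the pause and referral action for symptomatic and for asymptomatic suspected CTRCD, including what applies to the mild class in Table 12. Say whether the general rule in 7.2 on silent declines covers cardiac findings, and how the rule operates inside and after the 8-week DLT period. Replace the other statements with cross-references. The clinical content is for the sponsor and its cardiology adviser to set.

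The cost is protocol wording only. The reconciliation itself needs no added visit, test or patient, and no change to the statistical design.
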